### 9.3 Protocol Deviations/Violations

All protocol deviations will be tabulated using counts and percentages by category and specific deviation classification within each category by treatment group and overall, among all randomized subjects. Subjects who experienced more than one event for a given category or deviation will be counted only once for that category or deviation.

All protocol deviations will be available in a subject listing. Additionally, a listing of subjects excluded from ITT, Safety, PP, PK, and PD analysis sets will be presented. These two listings will list all subjects randomized into the study.

### 9.4 Demographics and Baseline Characteristics

#### 9.5 Demographics

Age at informed consent, sex, race, ethnicity, weight, height, BMI, and BMI category at baseline will be summarized descriptively [number of subjects (n), mean, SD, median, Q1, Q3, minimum, and maximum] for the ITT population.

#### 9.6 Medical History

Medical and surgical histories will be coded using MedDRA (Medical Dictionary for Regulatory Activities) version 25.0 and tabulated by System Organ Class and Preferred Term for all treatment groups and overall. Subjects with more than one reported history for a given System Organ Class or Preferred Term will be included only once in that category.

Medical history will be presented in a subject listing for the ITT population.

### 9.7 Prior and Concomitant Medications

Data for all prior and concomitant medications will be summarized with counts and percentages by treatment group and overall for the ITT population. Prior medications are defined as those with an end date before the date of informed consent. Concomitant medications are defined as those with an end date on or after the date of informed consent. Medications with missing end dates will have their end date imputed as “Continuing” and will therefore be considered as concomitant medications. Please refer to [Section 8](#), Statistical Considerations and Analysis, for further detail on imputed dates for prior and concomitant medications.

Prior and concomitant medications will also be presented in a subject listing for the ITT population.

### 9.8 Extent of Exposure

### 9.9 Treatment Duration and Compliance

For Cohorts 1-3, study treatment exposure and compliance will be summarized in the following manner:

- As a continuous summary of the number of doses received per subject
- As a categorical summary of the number of subjects receiving no, one, or both doses of IP
- As a categorical summary of the number of doses administered outside of the study window, and the count and percentage of subjects that received at least one dose out of the study window
- As a categorical summary of the reasons a dose was not administered

For Cohort 4, study treatment exposure and compliance will be summarized in the following manner:

- As a categorical summary of the number of subjects receiving no or one dose of IP
- As a categorical summary of the reasons the dose was not administered

The above summaries will be presented by treatment group and overall in the ITT population.

### 9.10 Analysis of Study Endpoints

#### 9.10.1 Primary Endpoint 1a – Adverse Events, Cohorts 1-4

In order to evaluate primary objective #1, to evaluate the safety and tolerability of repeat intramuscular (IM) administration of G03-52-01 in healthy adult subjects, primary endpoint #1a will be used:

The occurrence of adverse events (AEs) and serious adverse events (SAEs) following administration of G03-52-01 to the final visit

Adverse events (AEs) will be captured in a log at all scheduled visits from Baseline/Dosing [Visit 2 (Day 1)] through the end of study. Unless specified otherwise, AEs summaries will include all events starting from the date of initial administration of G03-52-01 up to and including the date of each subject’s final scheduled

## Statistical Analysis Plan (SAP)

---

study visit. AEs with a start date after subjects' final scheduled study visit will not be included in table summaries. All AEs captured in the database will be included in subject listings.

All AEs with the exception of reactogenicity events will be classified by Primary System Organ Class (SOC) and Preferred Term (PT) according to the Medical Dictionary for Regulatory Activities (MedDRA®) version 25.0. All AEs that occur after the initiation of study medication will be included in TFL summaries. Table summaries will include the frequency and percentage of subjects experiencing each event, as well as the total number of events experienced at each level of summarization (i.e., SOC and PT within SOC). The following summaries will be presented for all AEs, medically attended adverse events (MAAEs), and serious adverse events (SAEs) by SOC and PT and by treatment group and for all subjects:

- Overall (i.e., regardless of severity or relationship to treatment)
- By maximum severity grade (mild, moderate, or severe)
- By closest relationship to study medication

Additionally, an overall summary irrespective of SOC/PT categorization will be presented separately for all AEs with the exception of reactogenicity events. This overall summary will tabulate the number of subjects and events for: AEs, MAAEs, Grade 3 or greater AEs, AEs related to IP (possibly related or definitely related), Grade 3 or greater AEs related to IP (possibly related or definitely related), AEs with outcome of death, SAEs, SAEs related to IP (possibly related or definitely related), AEs leading to study discontinuation, AEs leading to discontinuation of IP, and AEs related to IP that led to discontinuation of IP.

Furthermore, a separate table will summarize the frequency and percentage of subjects experiencing each reactogenicity event and the total number of events experienced per term. The summary will be broken down by dose (i.e., Dose 1 and Dose 2) for Cohorts 1-3. Events that occur on or after date of first dose and before date of second dose will be summarized under Dose 1. Events that occur on or after date of second dose will be summarized under Dose 2. Reactogenicity events will be broken down into local reactions (injection site pain, injection site tenderness, injection site redness, injection site swelling) and systemic reactions (fever, headache, myalgia, abdominal pain, anorexia, nausea, vomiting, diarrhea, and malaise/fatigue).

Finally, three AE tables will be produced combining data across all four cohorts with the goal of comparing AE rates following initial administration of IP and before subjects in the first three cohorts received their second dose. For Cohorts 1-3, all AEs will be included that occur starting from the date of initial administration of G03-52-01 and prior to the date of each subjects' second dose. For Cohort 4, all AEs will be included that occur starting from the date of initial administration of G03-52-01 and prior to the date each subject's Day 45 study visit. If a Cohort 4 subject does not attend their Day 45 study visit, then all AEs will be included that occur up to and including 44 days from the subject's initial administration of G03-52-01. For these three AE summaries, Cohort 1 and Cohort 2 subject groupings will include both DP lots and the two Placebo groups (Cohorts 3 and 4) will be pooled together, such that the treatment groupings are as follows: Cohort 1, 50 mg (Both Lots); Cohort 2, 100 mg (Both Lots); Cohort 4, 100 mg; Cohorts 3 and 4, Placebo; and

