9.9. Methods and Timing for Assessing, Recording, and Analyzing Safety Parameters

9.9.1. Adverse Events

AEs will be collected at Day 1 during and after dosing. Any medical condition that is present at the time that the subject is screened should be considered as baseline and not reported as an AE. However, if the condition increases in severity or frequency at any time during the study, it should be recorded as an AE.

All AEs must be graded for severity and relationship to study product based on the Investigator’s assessment.

The Investigator will assess the intensity of AEs based on the following definitions per Toxicity Table (modified from FDA Toxicity Grading Scale for Healthy Adult and Adolescent Volunteers Enrolled in Preventive Vaccine Clinical Trials):

- Mild: Grade 1 (awareness of sign or symptom, but easily tolerated)
- Moderate: Grade 2 (discomfort sufficient to cause interference with normal activities)
- Severe: Grade 3 (incapacitating, with inability to perform normal activities)
- Potentially Life Threatening: (Grade 4)

- Death: (Grade 5)

It is important to distinguish between serious and severe AEs. Severity is a measure of intensity whereas seriousness is defined by the criteria in [Section 9.8.2](#).

An AE of severe intensity need not necessarily be considered serious. For example, nausea that persists for several hours may be considered severe nausea, but not an SAE. On the other hand, a stroke that results in only a limited degree of disability may be considered a mild stroke but would be an SAE.

For an AE to be a suspected drug-related event, there should be at least a reasonable possibility of a causal relationship between the study drug and the AE.

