11.5.3. Safety and Tolerability

All safety analyses will be based on the safety population, unless otherwise stated.

AEs will be coded using Medical Dictionary for Regulatory Activities® (MedDRA® Version 24.0). All AEs that occur after the initiation of study medication will be summarized using frequency counts and percentages. Summaries will be presented by treatment group. The following summaries will be presented for AEs and SAEs:

- Overall (i.e., regardless of severity or relationship to treatment)
- By severity grade (mild, moderate, or severe)
- By relationship to study medication
- By MedDRA® level hierarchy (system organ class and preferred term)

Unless otherwise specified, at each level of subject summarization in reporting the incidence of an AE, a subject will only be counted once if the subject reported one or more occurrence of an event. If more than one occurrence of an event is reported, the event of the worst severity or the worst-case relationship assessment will be summarized.

Vital signs (HR, BP, respiratory rate, pulse oximetry and body temperature), PEs, and clinical laboratory values, including change from baseline, will be summarized descriptively by treatment group, including both visit values and change from baseline (measured at admission) to each visit. In addition, shift tables, showing individual subject changes from baseline will be presented for laboratory parameters using toxicity grading. Subjects with graded values of vital

sign and laboratory parameters will be identified in listings, along with significant changes identified in the symptom-directed physical examinations.

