- A urine dipstick will be done to evaluate for presence of protein, glucose or blood in urine. If dipstick is abnormal (>+1), a complete urinalysis with microscopic will be performed.
- A 12-lead ECG will be done during screening. Subjects with a QTc interval >450 milliseconds will be excluded from participation.
- Viral Serology includes HIV, HBsAg and antibody to HCV.
- PK samples will be collected for all subjects at pre-dose, 2 hours (± 10 minutes), 4 hours (± 15 minutes), 8 hours (± 15 minutes), 24 hours (± 2 hour) post dose, and on Days 8, 15, 30, 45, 90, and 120.
- Serological samples (PD) will be collected for all subjects at pre-dose, 2 hours (± 10 minutes), 4 hours (± 15 minutes), 8 hours (± 15 minutes), 24 hours (± 2 hour) and on Days 30,45, and 90.
- ADA samples will be collected and tested for all subjects at pre-dose and post-dose on Days 90 and 120.
- PK samples will be collected at pre-dose, 2 hours (± 10 minutes), 4 hours (± 15 minutes), and 8 hours (± 15 minutes) post-dose.
- PD samples will be collected at pre-dose, 2 hours (± 15 minutes), 4 hours (± 15 minutes), and 8 hours (± 15 minutes) post-dose.
- Subjects will be provided with a reactivity diary prior to leaving the clinic on baseline/dosing Day 1. Subjects will be asked to complete daily diary records study Day 1-7 and diary is to be collected by site staff on Day 8 for review.

**APPENDIX B. TOXICITY TABLE OF CLINICAL ADVERSE EVENTS
(MODIFIED FROM FDA TOXICITY GRADING SCALE FOR
HEALTHY ADULT AND ADOLESCENT VOLUNTEERS ENROLLED
IN PREVENTIVE VACCINE CLINICAL TRIALS)**

Local Reaction to Injectable Product				
Clinical Abnormality	Mild (Grade 1)	Moderate (Grade 2)	Severe (Grade 3)	Potentially Life Threatening (Grade 4)
Pain	Does not interfere with activity	Repeated use of nonnarcotic pain reliever >24 hours or interferes with activity	Any use of narcotic pain reliever or prevents daily activity	ER visit or hospitalization
Tenderness	Mild discomfort to touch	Discomfort with movement	Significant discomfort at rest	ER visit or hospitalization
Erythema/redness	2.5 – 5 cm	5.1 – 10 cm	> 10 cm	Necrosis or exfoliative dermatitis
Induration/swelling	2.5 – 5 cm and does not interfere with activity	5.1 – 10 cm or interferes with activity	> 10 cm or prevents daily activity	Necrosis
Systemic (General)				
Clinical Abnormality	Mild (Grade 1)	Moderate (Grade 2)	Severe (Grade 3)	Potentially Life Threatening (Grade 4)

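### No AE table specified in SAP 9.10.1 is required to show reactogenicity events by severity grade or relationship, although the protocol plans AE summaries by both

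*SAP*

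**What the plan says.** SAP 9.10.1 sets out the analysis of primary endpoint 1a in the Safety population. It makes three provisions for reactogenicity events.

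- **Coding.** "All AEs with the exception of reactogenicity events will be classified by Primary System Organ Class (SOC) and Preferred Term (PT"; the rest of the sentence gives the MedDRA version. The tables by maximum severity and by relationship are built on these codes.
- **Overall table.** "an overall summary irrespective of SOC/PT categorization will be presented separately for all AEs with the exception of reactogenicity events". Its rows include medically attended AEs (MAAEs), Grade 3 or greater AEs, IP-related AEs, Grade 3 or greater IP-related AEs, SAEs, deaths and discontinuations.
- **Their own table.** "a separate table will summarize the frequency and percentage of subjects experiencing each reactogenicity event and the total number of events experienced per term". In addition, "The summary will be broken down by dose (i.e., Dose 1 and Dose 2) for Cohorts 1-3", and the terms are grouped as local or systemic.

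Other wording in the section points the other way. Every post-dose AE is to be in the TFL summaries, the coded tables are described as covering all AEs, and all AEs are listed by subject. Three further tables for the first 45 days are to include all AEs, with no exclusion stated.

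On the protocol side, 9.9.1 says "All AEs must be graded for severity and relationship to study product". Section 11.5.3 says "All AEs that occur after the initiation of study medication will be summarized using frequency counts and percentages", and plans summaries of AEs and SAEs by severity and by relationship without excepting reactogenicity. Appendix B has a block headed "Local Reaction to Injectable Product" with Grades 1 to 4 for pain, tenderness, redness and swelling, followed by a graded systemic block. SAP Section 10, on changes from the protocol, reads N/A.

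**The concern.** Tolerability of an intramuscular injection is part of the first primary objective, and local and early systemic reactions bear directly on it. If these events are only counted, a mild ache and a reaction that prevents daily activity add the same amount to the table.

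Meanwhile the main overall summary reports Grade 3 or greater and IP-related totals that leave these events out. The omission can lower those totals or leave them unchanged, but cannot raise them. If the product causes reactions, it lowers them more in the active groups than on placebo, so the comparison between groups is affected as well as the level.

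**Working it through.** The plan states no figure on this point to reproduce. The check is a trace of the displays in SAP 9.10.1, a comparison with the protocol, and an illustration of scale.

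**1. Which displays hold reactogenicity events, and which show grade or relationship**

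| Display | Holds reactogenicity events? | Shows grade or relationship? |
|---|---|---|
| Coded tables by severity and by relationship | No row, by implication (events uncoded) | Yes |
| Overall AE summary | Expressly excluded | Yes |
| Reactogenicity table | Yes | No |
| First-45-day overall summary | Unclear: all AEs, no exclusion stated | Rows not specified |
| First-45-day coded tables by severity and by relationship | Said to include all AEs, but uncoded events have no row | Yes |
| Subject listings | Yes | Individual data, no group rates |

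No table has a clear yes in both columns. Only the first-45-day overall summary could have one. For Cohorts 1-3 it stops before the second dose, so it cannot cover Dose 2 reactions in any case.

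**2. Comparison with the protocol**

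The SAP's own phrasing, AEs with an exception for reactogenicity, treats these events as a subset of AEs. Protocol 9.9.1 and 11.5.3 then apply to them: graded, attributed, and summarised by severity and relationship. The SAP does not do this, and its Section 10 does not declare the difference.

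**3. Whether grade definitions exist**

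The SAP lists 4 local and 9 systemic terms, 13 in all. Three (abdominal pain, anorexia, diarrhea) have no Appendix B row. The other 13 - 3 = 10 do, with nausea and vomiting sharing one row. For the three without a row, protocol 9.9.1 gives general definitions of mild, moderate, severe and potentially life threatening.

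**4. Scale, under assumed rates**

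Planned active subjects (SAP 3.1): n = 150 + 150 + 200 = 500. The documents give no rate p of Grade 3 or 4 reactions, so a range is assumed. Expected number = n × p; P(at least one) = 1 - (1 - p)^n.

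| Assumed p | Expected subjects | P(at least one) |
|---|---|---|
| 0.5% | 2.5 | 0.918 |
| 1% | 5 | 0.993 |
| 2% | 10 | >0.999 |
| 5% | 25 | >0.999 |

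These subjects would be counted in the reactogenicity table, but nothing in it would identify them as Grade 3 or 4.

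**The case against.** The best defence is that the primary endpoint is the occurrence of AEs, and occurrence of each reaction is tabulated by term. There is no hypothesis test (protocol 11.1, SAP Section 6), so no estimate or decision rule changes. The overall summary is openly defined as excluding reactogenicity. The table shells are in a separate document (SAP Section 1) and may show grade. Protocol 14.2 also lists reactogenicity data separately from AEs, so relationship may never have been recorded for diary events.

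Part of this stands. The shells were not available, so the finding is about what the SAP requires, not about what will be programmed. Whether relationship was recorded for diary events is unknown. The rest does not remove the gap: protocol 11.5.3 plans severity and relationship summaries for AEs as well as counts, listings give no group rates, and the sentence placing all AEs in the TFL summaries conflicts with the exclusion without resolving it. The worst-severity rule says which occurrence to count; it does not add a grade breakdown to a table that has none.

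A reader might infer more than the documents support:

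- *Reactogenicity is removed from every AE table.* The only table with an express exclusion is the main overall summary. The first-45-day tables state none.
- *Severe reactions appear in no summary, or only as present or absent.* They are counted in the reactogenicity table, with event totals by term and a split by dose in Cohorts 1-3. Their grade and relationship are what is missing.
- *A cluster of severe reactions would escape the halting rules.* Halting rests on review by the medical monitor with the sponsor's medical lead, and by the DSMB (protocol 9.12.1), not on final tables. The DSMB receives AE incidences and listings (SAP 4.2).
- *Arthralgia, graded in Appendix B, is lost.* It is not on the SAP's reactogenicity list, so if reported as an AE it would be coded and tabulated.

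**Conclusion.** The concern holds in limited form. As SAP 9.10.1 is written, no table has to show reactogenicity events by grade or relationship. The main summary's Grade 3 or greater, IP-related, MAAE and SAE rows omit them, and it is unclear whether the first-45-day overall summary includes them. This is an undeclared departure from protocol 9.9.1 and 11.5.3, on the tolerability part of the first primary objective.

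The size cannot be computed from the documents. Across assumed rates of 0.5% to 5%, between 2.5 and 25 of 500 active subjects would be expected to have a Grade 3 or 4 reaction not identifiable as such in any specified table. The conclusion assumes that reactogenicity events are AEs, as the SAP's wording implies, and that the shells add nothing beyond the SAP text. Neither the study design nor the safety oversight is called into question.

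**What to change.** In SAP 9.10.1:

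1. Tabulate each reactogenicity term by maximum severity grade, by dose and treatment group. Use the Appendix B row where one exists, and the general definitions in protocol 9.9.1 for abdominal pain, anorexia and diarrhea. Add rows for any local reaction, any systemic reaction and any reaction of Grade 3 or greater.
2. Add to the overall summary a version of the Grade 3 or greater, MAAE and SAE rows that includes reactogenicity events. Do the same for the IP-related rows where relationship was recorded.
3. State whether the three first-45-day tables include reactogenicity events, and reconcile this with the sentences that place all AEs in the summaries.
4. Either align with protocol 11.5.3 or declare and justify the departure in Section 10.

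The cost is SAP wording and one or two table shells, with no design change. Reported Grade 3 or greater and related rates may look slightly less favourable.

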5. INVESTIGATIONAL PLAN

5.1. Study Design

This is a Phase 2, multicenter, randomized, double-blinded, placebo-controlled study to evaluate the safety, tolerability, pharmacodynamics (PD), and immunogenicity of a single dose (100 mg) and a repeat dose (50 mg and 100 mg) of G03-52-01 administered by IM injection(s) in adult subjects ([Appendix C](#)).

Approximately 625 subjects will be enrolled in this study to receive active product or placebo on Day 1 or Day 1 and Day 45, and will be randomized to the following concurrent cohorts:

- Cohort 1 (N=150, 75 lot #1, 75 lot #2): 50-mg dose
- Cohort 2 (N=150, 75 lot#1, 75 lot#2): 100-mg dose
- Cohort 3 (N=75): Placebo
- Cohort 4 (N=250): 100 mg dose or Placebo

The study will include up to 14-day screening period and an approximately 1-hour stay for Cohorts 1-3 and 8 hours stay for Cohort 4 in the clinic after dosing is complete for PK assessment and to ensure that no hypersensitivities or safety signals occur. Follow-up visits will occur at 24 hours and 72 hours post dose, and on Days 8, 15, 45, 49, 60, 90, 120, 150, 180, and 240 for Cohorts 1-3. For Cohort 4, follow-up visits will occur 24 hours, 72 hours, and on Days 8, 15, 30, 45, 90, and 120.

Safety Analysis

Safety labs will be drawn at pre-dose, 24 hours post dose, and on Days 15, 45 (before repeat-dose or placebo), 60, 120, and 240 for Cohort 1-3. Subjects in Cohort 4 will have safety labs drawn at screening and on Day 15, 45, and 120.

PD Analysis

PD samples will be collected for all subjects. Analysis will be completed by the Battelle Mouse Neutralization Assay (MNA) for Serotypes A and B.

Samples for subjects in Cohorts 1-3 will be tested at pre-dose, 24 hours post dose, and on Days 8, 15, 45 (before repeat-dose or placebo), 49, 90, and 120. The first 25 subjects randomized for each DP lot of 50 mg and 100 mg doses and placebo will be tested at all 8 timepoints. The remaining samples from the subjects who received either dose or lot of G03-52-01 (including placebo) will only be tested using MNA at pre-dose and Days 45, 90, and 120.

All subjects in Cohort 4 will have samples collected at pre-dose, 2 hours, 4 hours, 8 hours, 24 hours and on Days 30, 45, and 90. Samples will be analyzed for the first 30 subjects in Cohort 4, who receive active drug and complete the sample collection at 24 hours. See [Figure 2](#) and [Figure 3](#).

PK Analysis

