9.1.7. Visit 7/ Day 45 (± 3 Day) Repeat Dose Period

- Obtain vital signs
- Review and update concomitant medications

- Review and assessment of AEs and SAEs
- Perform symptom-directed PE
- Obtain blood samples (prior to administration of G03-52-01 or Placebo) for the following:
 - PK
 - MNA
 - ADA
 - Clinical safety labs
 - Hypersensitivity panel
 - Future use (if consent given)
- Distribute reactogenicity diary
- Obtain pregnancy test
- Obtain urine dipsticks
- Obtain urine sample for toxicology
- Perform Breathalyzer test to detect recent alcohol use
- Counsel women of child-bearing potential on the avoidance of pregnancy
- Counsel the subject not to receive any botulinum toxin preparation (e.g., Botox) for 4 months after injection
- Counsel the subject on eligibility to receive any authorized COVID-19 vaccine 8 days after visit

Administration of repeat 50 mg or 100 mg G03-52-01 dose or placebo IM injection. Subjects will be observed at the study site for approximately 1 hour after dose administration.

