9.8.1. Adverse Events

ICH E6(R2) defines an AE as any untoward medical occurrence in a patient or clinical investigation subject administered a pharmaceutical product and which does not necessarily have a causal relationship with this treatment. An AE can therefore be any unfavorable and unintended sign (including an abnormal laboratory finding), symptom, or disease temporally associated with the use of medicinal (investigational) product, whether or not related to the medicinal (investigational) product.

FDA defines an AE as any untoward medical occurrence associated with the use of a drug in humans, whether or not considered drug related.

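### The three first-45-days AE tables compare cohorts with two counted safety-laboratory draws against a cohort with one, so laboratory-detected AEs can look less frequent in Cohort 4 with no true difference.

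*SAP*

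**What the plan says.** SAP 9.10.1 states that "three AE tables will be produced combining data across all four cohorts with the goal of comparing AE rates following initial administration of IP". The three tables are an overall summary, one by organ class, preferred term and maximum severity, and one by organ class, preferred term and closest relationship. The columns are Cohort 1 and Cohort 2 (lots combined), Cohort 4 active, placebo from Cohorts 3 and 4 pooled, and a total.

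For Cohorts 1-3 the window runs from the first dose "and prior to the date of each subjects' second dose". For Cohort 4 it runs from the dose "and prior to the date each subject's Day 45 study visit" or, if that visit is missed, "up to and including 44 days from the subject's initial administration".

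Protocol 5.1 gives the laboratory schedules. For Cohorts 1-3: "Safety labs will be drawn at pre-dose, 24 hours post dose, and on Days 15, 45 (before repeat-dose or placebo), 60, 120, and 240". Cohort 4 follows a different one: "Subjects in Cohort 4 will have safety labs drawn at screening and on Day 15, 45, and 120". The AE definition in Protocol 9.8.1 extends to untoward signs, "including an abnormal laboratory finding".

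SAP 9.10.1 contains no restriction, separate row or footnote for the different laboratory schedules.

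**The concern.** A table built to compare AE rates needs similar opportunities to detect AEs in each column. SAP 9.10.1 takes care over the calendar window, down to missed Day 45 visits, but leaves the laboratory looks inside it unequal.

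Cohort 2 and Cohort 4 active both receive 100 mg, from different lots, and stand as separate columns. These are the only AE tables whose stated goal is this cross-cohort comparison. A laboratory change that appears a day after injection and resolves by Day 15 can be caught at a scheduled draw in Cohort 2 but not in Cohort 4. A reader could take the resulting gap for a lot difference. The pooled placebo column does not help, because it blends both schedules and matches neither active column.

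**Working it through.** The plan states no laboratory-AE rate or expected ratio, so there is no figure of that kind to reproduce. The group sizes do reproduce: 375 at 2:2:1 gives 150, 150 and 75; 250 at 4:1 gives 200 and 50; the total is 625, as in SAP Table 1.

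**Step 1: count the draws inside the window** (Protocol 5.1, 9.1.3, 9.1.6, 9.1.7, 9.2.3, 9.2.6, 9.2.8)

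| Post-dose safety draw | Cohorts 1-3 | Cohort 4 |
|---|---|---|
| 24 hours | yes | no (PK and MNA blood only) |
| Day 15 | yes | yes |
| Day 45 | outside the window | outside the window |
| Counted | 2 | 1 |

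In Cohorts 1-3 the Day 45 blood is taken at the second-dose visit ("Obtain blood samples (prior to administration of G03-52-01 or Placebo) for the following"), so a finding with that date is not before the date of the second dose. In Cohort 4 the window also ends before the Day 45 visit date. SAP 9.10.1 gives no end date for a Cohorts 1-3 subject who never has a second dose; such subjects are left aside here.

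**Step 2: direction.** Day 15 is common to all cohorts. If the chance of a finding at Day 15 is the same everywhere, the chance of a finding at 24 hours or Day 15 cannot be lower than at Day 15 alone. Scheduled-laboratory AEs can therefore only look equal or fewer in Cohort 4.

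**Step 3: size.** Assumptions, not in the documents: per-draw probability p, between-draw correlation r, and no drug or lot effect.

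- One draw: p.
- Two draws: 2p − [p² + r·p(1−p)].
- Ratio, Cohort 4 to Cohort 2: 1 / [2 − p − r(1−p)].

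At p = 5%:

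| r | Cohort 2 | Cohort 4 | Ratio |
|---|---|---|---|
| 0 | 9.75% | 5.0% | 0.51 |
| 0.25 | 8.56% | 5.0% | 0.58 |
| 0.5 | 7.38% | 5.0% | 0.68 |
| 0.75 | 6.19% | 5.0% | 0.81 |
| 1 | 5.0% | 5.0% | 1.00 |

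At r = 0 the expected counts are 14.6 of 150 and 10 of 200. Varying p from 1% to 20% at r = 0 moves the ratio only from 0.50 to 0.56, so persistence matters more than the rate.

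With unequal yield (independent draws, Day 15 at 5%, 24-hour yield k times that), the ratio is 0.05 / [1 − (1 − 0.05k)(0.95)]: 0.81 for k = 0.25, 0.68 for k = 0.5, 0.35 for k = 2 and 0.21 for k = 4.

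**Step 4: pooled placebo.** At p = 5% and r = 0: (75 × 9.75% + 50 × 5.0%) / 125 = 7.85%. With an inert product, Cohort 2 is then 9.75 / 7.85 = 1.24 times placebo and Cohort 4 is 5.0 / 7.85 = 0.64 times placebo, from scheduling alone.

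**Step 5: any-AE rows.** Suppose 20% to 40% of subjects have a non-laboratory AE, independent of laboratory AEs, and p is 2% to 10% with r = 0. The ratio for any AE is then 0.80 (28.0% against 35.2%) to 0.97 (41.2% against 42.4%).

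**Step 6: test the remedy.** If findings seen only at 24 hours are left out, every column rests on Day 15 and the null ratio is p / p = 1.00. A simpler rule, dropping every laboratory AE that starts at the 24-hour draw, overcorrects. At p = 5% and r = 0.5 the chance of a finding at both draws is 0.25% + 2.375% = 2.625%. Cohorts 1-3 would keep 5% − 2.625% = 2.375% against 5% in Cohort 4, a ratio of 2.1 in the other direction.

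**The case against.** The strongest case on the other side concerns size and net direction. A reader might infer from two draws against one that laboratory AEs will look half as frequent in Cohort 4, or that the tables as a whole favour the new lot. The documents support neither.

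- *Half.* This needs equal yield at both draws, independence, and abnormalities too brief to be seen twice. None of these is stated, and full persistence removes the gap.
- *Overall direction.* Cohort 4 has an 8-hour stay (Protocol 9.2.2) and a Day 30 visit with AE review (9.2.7). Cohorts 1-3 have a 1-hour stay and no visit between Day 15 and Day 45. These can raise Cohort 4's count of other AEs, while the Day 15 ECG can raise that of Cohorts 1-3. The net any-AE bias is unknown. None of these contacts adds a safety-laboratory draw, so the laboratory imbalance stands.

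Other points carry some weight:

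- SAP 9.10.2 summarises laboratory values and shifts by visit, so Day 15 results can be read like for like. That does not correct the AE tables.
- Two of the three tables list preferred terms, so laboratory terms appear on their own rows. Those rows still compare two looks with one.
- No hypothesis test is planned (SAP 6), and Cohort 4 was randomised separately (SAP 3.3), so the comparison is descriptive. Comparison is nevertheless the stated purpose, and a percentage can mislead without a test.
- Protocol 9.8.1 allows a laboratory finding to be an AE but does not make every graded value one. The laboratory share of AEs is unknown.
- The SAP cites protocol version 5.0 of 06-JAN-2025, while the protocol supplied is dated 12 Apr 2024. The Cohort 4 schedule should be confirmed against version 5.0.

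**Conclusion.** The point holds for laboratory-detected AEs. Inside the comparison window Cohorts 1-3 have two counted safety-laboratory draws and Cohort 4 has one, and SAP 9.10.1 makes no allowance for it. With no true difference and the same chance of a finding at Day 15, scheduled-laboratory AEs look equal or fewer in Cohort 4, never more.

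The size depends on assumptions that the documents do not settle. With equal yield at the two draws the ratio lies between about 0.5 (transient, independent) and 1.0 (fully persistent). It falls below half if abnormalities cluster at 24 hours. The pooled placebo column carries a mixture of the two schedules. For all AEs taken together no direction can be claimed.

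**What to change.** In SAP 9.10.1, for the three across-cohort tables only:

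- Keep the all-AE rows as planned.
- Add rows that leave out laboratory AEs in Cohorts 1-3, including Cohort 3 placebo, that were detected at the 24-hour draw and were no longer present at the Day 15 draw. Findings still present at Day 15 stay in. Use these rows for the cross-cohort comparison, and state how a missing Day 15 result is handled.
- Show the excluded events in a separate row labelled as detected only at 24-hour labs, Cohorts 1-3.
- Show placebo by cohort as well as pooled.
- Footnote the differing laboratory and visit schedules.

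The whole-study AE tables and listings do not change.

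No new data are needed. The cost is a short SAP addition, a programming flag and a few extra rows. It also needs a classification, made blind to treatment, of which AE terms are laboratory-detected. The AE fields in Protocol 9.10.1 do not record how an event was detected, and a matching start date alone cannot separate a laboratory AE from a clinical one that began the same day.
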